### 9.4.2 ANALYSIS OF THE PRIMARY EFFICACY ENDPOINT(S)

To test for significant differences in the incidence of UTIs across periods, as mentioned above, paired samples t-tests will be conducted using log-transformed infection rates rather than the raw rates. We may then subsequently re-analyze this data using a Generalized Linear Mixed Model (GLMM) with log link and a Poisson distribution, as is appropriate for count outcomes data.

### 9.4.3 ANALYSIS OF THE SECONDARY AND TERTIARY ENDPOINT(S)

To assess the impact of the study intervention on our Secondary Endpoint, bladder, and bowel complications (Hypothesis 2), and Tertiary Endpoints, QOL (Hypothesis 3), and Participation (Hypothesis 4), a similar analytic approach will be used as was used for Hypothesis 1. The outcomes for these hypotheses are all continuous and therefore paired t tests or GLMM will be used. Our plan for handling missing data across all study analyses will include the use of common statistical methods to handle missing data such as multiple imputation and the estimation maximization approach. As appropriate, we may employ sensitivity analysis to assess the effect of data that is not missing at random such as when participants stop using the research treatment but continue to be willing to participate in the study's assessments.

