## 4.2 SCIENTIFIC RATIONALE FOR STUDY DESIGN

This study's pre-post design is selected because it provides substantially more statistical power than a parallel group design with a similar sample size and allows participants to serve as their own controls, without requiring them to use placebo for half of the study. Our prior project experience, using a cross-over design indicated that subjects are likely to drop out if they think that they are receiving placebo.

- Treatment (gentamicin plus saline) is administered to each study participant for six months.
- This design provides the benefit of a direct comparison within participants (the effect of no treatment vs. treatment).
- Superiority trial – this design allows one to determine a clinically relevant difference between no intervention and the study intervention.

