- We anticipate the ability to screen at least 30-50 participants in order to obtain a sample of 25 potential participants following eligibility screening with the goal of enrolling and retaining a minimum of 15 participants..
- Special efforts will be made to recruit minority participants by ensuring that all potential eligible minority participants are contacted and invited to participate.

---

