## 7 STUDY INTERVENTION DISCONTINUATION AND PARTICIPANT DISCONTINUATION/WITHDRAWAL

### 7.1 DISCONTINUATION OF STUDY INTERVENTION

Participants may elect to discontinue the study intervention for any number of reasons (not inclusive list): burden of study procedures, side effects, caregiver limitations, etc. They will be educated on signs and symptoms of toxicity (see Section 8.2) and instructed to notify the study team and their physician for advice on discontinuation of study treatment. If a participant develops COVID-19 while participating in this study, the study team will make every effort to keep the participant in the trial. Participants with COVID-19 will remain in the study unless, for medical reasons, they can no longer participate.

Participants will be asked about the reasons for withdrawal from the study when self-initiated.

Regardless of the reason, discontinuation of the study treatment does not mean withdrawal from the study since the study uses an intent –to-treat design. If a participant decides to stop using the study product, and they are willing, they will remain enrolled in the study. This means that study procedures, including bi-weekly phone calls and study visits will go on as scheduled. No drug taper is required when subjects discontinue the study treatment – they may stop immediately. These subjects will also complete the study's final assessments, if willing.

Regarding the discontinuation of treatment, the following information will be documented in the study record:

- Reason for discontinuation of intervention (i.e. treatment).
- Date of last dose.
- Willingness to continue in the study.

If a participant decides to discontinue the study intervention in light of a new or exacerbated clinical finding, we will report the finding on the Adverse Event case report form, and report to the necessary entities as outlined in the Events Reporting Schedule.

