**Statistical Analysis Plan**

**6/23/2023**

### **Statistical Analysis Plan**

All data were examined for completeness and outliers before hypothesis testing. Categorical data was summarized in terms of frequencies, presented as n (%), and continuous data will be summarized in terms of means (standard deviations). Participant demographics and clinical status were evaluated using descriptive statistics. All efforts were made to recruit a balanced sample representative of persons with SCI/D. Statistical significance was set at  $p < 0.05$  for group comparisons with a 95% confidence interval.

To test for significant differences in the incidence of UTIs across periods (six months pre-treatment, six-month treatment, one-month post-treatment, six months post-treatment) an incidence rate per person month was determined by comparing the total number of UTIs in relation to duration, reflecting all participants across six months. The incidence rate ratio was determined by comparing the different timepoint ratios in relation to pre-treatment ratio. Confidence intervals and p values were calculated for rates and rate ratios. This approach analytical was used to satisfy small sample size calculations, as appropriate with count outcomes data (Hypothesis 1). To assess the impact of the study intervention on our Secondary Endpoint, bladder, and bowel complications (Hypothesis 2), and Tertiary Endpoints, QOL (Hypothesis 3), paired t tests were used to test differences in scores across survey measures.

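### The optional not-missing-at-random analysis is illustrated by participants whose scores are observed; those with no Visit 2 score get no such check, which can overstate the survey gains if they do worse

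*Protocol*

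**What the plan says.** Protocol 9.4.3 handles missing survey data with "common statistical methods to handle missing data such as multiple imputation and the estimation maximization approach". No imputation model, auxiliary variables or scenario is given. It then adds an optional step ("As appropriate, we may employ sensitivity analysis"). The step is described as a "sensitivity analysis to assess the effect of data that is not missing at random such as when participants stop using the research treatment", and the example ends with "but continue to be willing to participate in the study's assessments". It is the only example given.

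Section 7.1 says of such people: "If a participant decides to stop using the study product, and they are willing, they will remain enrolled in the study". Their calls and visits continue, and they do the final assessments if willing.

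Section 8.1 and the schedule in 1.3 place the survey measures at two times only, baseline and about six months (Visit 2). Section 7.3 lets medical-record data stand in when the second visit cannot be completed. Its example is UTI treatment, and the record is not presented as a source of survey scores.

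Section 9.3 defines a primary population by use of the flushes on at least half of the days, with UTI data available, and adds an intent-to-treat analysis of available data. Section 9.4.7 foresees a review of the characteristics of completers and non-completers.

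The SAP says of the survey endpoints only that "paired t tests were used to test differences in scores across survey measures". It names H2 and H3 there, not H4, and mentions neither imputation nor sensitivity analysis.

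**The concern.** The sensitivity analysis is the only place where the plan allows for loss that depends on the unseen outcome, and its one example is a group whose outcomes are seen. The group whose outcomes are not seen, called leavers here, started treatment but have no Visit 2 score. Nothing in either document tests what happens if they did worse than those who stayed.

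The survey results for H2 to H4 are before-after changes in one arm. There is no control group in which similar losses might partly cancel, and no intermediate score to show how a leaver was doing. If leaving is linked to a poor response, the completers' change overstates the change among all who started.

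**Working it through.** **The plan's own figure.** There is none to reproduce. The 15 completers in section 9.2 are for UTI rates. No effect size is given for the survey scores, and no attrition rate for anything.

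**Step 1. Who is observed and who is missing.**

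| Participant | Visit 2 score | Protocol | SAP |
|---|---|---|---|
| Stays on drug, attends | observed | used | used |
| Stops drug, attends | observed | the 9.4.3 example | usable in a paired t-test |
| No Visit 2 score | missing | MI or EM, unspecified | no pair, so not in the t-test |

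**Step 2. What a missing-at-random method does here.** If imputation uses only the baseline score, it fits Visit 2 on baseline among completers and applies that line to leavers. With similar baselines, leavers receive about the completers' mean change. A mixed model fitted to the two visits keeps the leavers' baseline scores but rests on the same assumption.

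**Step 3. Size of the possible bias.** Let d be the share of starters with no Visit 2 score, g the completers' mean gain, and f the leavers' mean gain as a fraction of g.

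- All-starter gain = (1 − d)g + d·f·g
- Completer gain ÷ all-starter gain = 1 / [(1 − d) + d·f]

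Both d and f are assumptions; d is taken from 10% to 40%. For example, d = 0.4 and f = 0 give 1/0.6 = 1.67; d = 0.4 and f = 0.5 give 1/0.8 = 1.25.

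| d | f = 0 | f = 0.5 | f = 1 | f = 1.5 |
|---|---|---|---|---|
| 10% | 1.11 | 1.05 | 1.00 | 0.95 |
| 20% | 1.25 | 1.11 | 1.00 | 0.91 |
| 30% | 1.43 | 1.18 | 1.00 | 0.87 |
| 40% | 1.67 | 1.25 | 1.00 | 0.83 |

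**Step 4. Check by simulation.** All inputs are assumed: 25 starters, completer gain 0.5 SD, baseline to Visit 2 correlation 0.6, loss unrelated to baseline, 1,500 runs, imputation from baseline only. Complete pairs and imputation agreed within 0.01 SD in every scenario. With leavers gaining nothing:

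| d | True all-starter gain | Complete pairs | Imputation | Imputation shifted by the true shortfall |
|---|---|---|---|---|
| 20% | 0.40 | 0.49 | 0.49 | 0.39 |
| 40% | 0.30 | 0.51 | 0.51 | 0.31 |

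The last column uses a shortfall known only inside a simulation. It shows that a shift of the right size removes the bias, not that the size can be learned from the data. The zero-change result needs no such knowledge: it is (1 − d) times the completer gain, here 0.8 × 0.49 = 0.39 and 0.6 × 0.51 = 0.31.

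**The case against.** Several stronger readings are tempting, and the documents do not support them.

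- **That the plan does inflate the gains.** No leaver outcomes are given. The last two columns of the first table show no bias or understatement if leavers gain as much or more. Only the conditional statement stands.
- **That the protocol shows loss to depend on perceived benefit.** Section 4.2 reports that "subjects are likely to drop out if they think that they are receiving placebo", but this comes from the abandoned cross-over design and is given as a reason for removing placebo. Everyone now knowingly receives gentamicin. The reasons for stopping listed in 7.1 are burden, side effects and caregiver limitations. They could relate to outcome, but that is not shown.
- **That 15 of 25 is a 40% attrition rate.** Section 5.5 speaks of 25 potential participants after screening "with the goal of enrolling and retaining a minimum of 15 participants". The gap mixes people who never start with people who leave, and those who never receive the intervention are replaced (7.2). The 40% here is only the top of an assumed range.
- **That imputation must give leavers the completers' change.** The contacts every two weeks record UTIs, adverse events and compliance (1.3, 6.4, 8.1), and the reason for stopping is documented (7.1). An imputation model could use these. The protocol does not rule them out, but does not commit to them either; the simulation covers baseline-only imputation.
- **That the SAP declares a complete-case analysis.** It is silent on missing data, and 9.4.3 says its missing-data plan covers all study analyses. It remains true that a paired t-test uses only participants with both scores.

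Two further points have weight. The example is introduced as an illustration of an optional analysis, so a team could still aim it at leavers; but then nothing is committed. And if the half-of-days population in 9.3 applies to the surveys, which is unclear, measured stoppers may fall outside it, and checking their influence is sensible. That is a question about treatment discontinuation, and it leaves participants without a score untouched. Offering the surveys by phone (7.3) should reduce their number, and the review in 9.4.7 may describe them, but neither tests the result against unfavourable outcomes.

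**Conclusion.** The point holds in conditional form. The only example in 9.4.3 concerns observed scores. Participants with no Visit 2 score have unspecified MI or EM in the protocol and no place in the SAP's paired t-tests. If they do worse than completers, the survey gains for H2 to H4 can be overstated: over an assumed 10% to 40% loss, by 1.11 to 1.67 times if leavers gain nothing and 1.05 to 1.25 times if they gain half as much. These ratios take the mean gain of all starters as the target, which suits the intent-to-treat analysis. Neither the direction nor the size can be settled from the documents. This is a cheap improvement to the secondary and tertiary analyses; it does not bear on the primary UTI comparison.

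**What to change.** In protocol 9.4.3 and in the SAP:

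1. State that Visit 2 scores observed after stopping the drug are used as they stand in the intent-to-treat analysis, and say whether the half-of-days population in 9.3 applies to the survey endpoints.
2. Aim the sensitivity analysis at participants who started treatment but have no Visit 2 score. First set their mean change to zero, keeping residual variation in the imputations so that the standard error is not too small. Then shift their change step by step until the conclusion alters, and report that tipping point.
3. Beside each survey t-test, report the number with no Visit 2 score, the reasons, and the zero-change result. Cover H4, which the SAP's sentence omits.
4. If imputation is kept, name its variables; the records from the two-weekly contacts are natural candidates.

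The cost is a short paragraph and a few lines of output per endpoint, and the reported gains may look smaller. The SAP is written mostly in the past tense, so if the analyses are already done, the added results should be labelled post hoc.

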### 9.4.4 SAFETY ANALYSES

The study team will ask about adverse events at the bi-weekly phone calls. The frequency of events will be monitored by the study coordinator and reported to the PI and co-Investigators at regular meetings. Instances in which the frequency of total events or of any event seem higher than expected will be referred to the DSMB for further review.

In the event that any participant dies during their study participation, the investigators will determine if this is related to the study intervention and document the cause of death regardless. The DSMB will be provided with this information along with that about other adverse events.

---

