## 8.2 SAFETY AND OTHER ASSESSMENTS

- The bi-weekly phone encounters and EMR reviews are the primary means of monitoring the occurrences of side effects and participant tolerability of the Gentamicin treatment. If a participant reports a UTI or UTI symptoms, they will be advised to follow-up with their personal provider for management. Any potential manifestation of gentamicin toxicity will also be assessed during these phone encounters. These include new onset and prolonged numbness, skin tingling, dizziness, and vertigo. They also include prolonged muscle twitching, tinnitus, roaring in the ears or hearing loss. The study team will recommend subjects with these symptoms be seen by a physician for otological assessment and possible study treatment discontinuation.
- A complete blood count and comprehensive metabolic panel will be administered at baseline and six months when treatment is concluded.
- If a study-ordered urine analysis (at screening, and approximately 6-months later, defined here with a window of plus or minus 30 days) reveals an infection, participants will be instructed to follow-up with their personal provider to treat the current infection. The results of the urine test will be included in the EMR and be available to providers across institutions with EPIC access.
- During the follow-up interview (3-months post-treatment), the participant will also be asked if they have used any gentamicin instillations since being off the study drug. If they have used gentamicin, they will be asked if they are still using it. If they have not used gentamicin, they will be asked why not.

- After the follow-up interview, participants will be thanked for their participation in the trial and asked to participate in a final optional survey. If willing, they will be asked about their perceptions of the benefits and/or challenges of using Gentamicin instillations and whether they thought their participation in this trial was worthwhile. This information will be recorded in their CRFs. This option will be offered to participants at the end of their 3-months post-treatment interview and/or at a different time following this interview, depending on their availability and interest in participating.

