## 8.3 ADVERSE EVENTS AND SERIOUS ADVERSE EVENTS

### 8.3.1 DEFINITION OF ADVERSE EVENTS (AE)

This study's definition of AE will align with the FDA definition: "any untoward medical occurrence associated with the use of a drug in humans, whether or not considered drug related." In practice, this means we will consider and document any experience or unfavorable and unintended sign, symptom, or disease that arises while an individual is participating in the study. This interpretation includes positive test results on urine analysis and urine culture (both those provided by the study and those ordered by the participant's treating physician) and reports of UTI symptoms (e.g., malodorous and cloudy urine, fatigue, fever, chills, etc.)

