### 9.2 SAMPLE SIZE DETERMINATION

Power calculations were conducted based on the **primary hypothesis that incidence of UTIs will be significantly lower during the treatment period (gentamicin + saline) than during the prior six months.**

In calculating power, we assume that during the study period, there will be a 50% reduction in UTIs from the number that participant experienced during the prior six months, which serves as the control period. These assumptions are based on the findings of a six-month retrospective study of gentamicin. Calculations of power were conducted assuming that paired samples t-tests will be used to assess the first hypothesis. While we may consider using other additional ways of determining differences in UTIs between the baseline and trial periods, paired samples t-tests will be used at least initially. Because we are working with count rather than continuous data, the t-tests will be conducted using natural log-transformed infection rates rather than the raw rates. Based on our assumptions, the sample size needed to have a power of at least 80% will be 15. This is the necessary sample size of participants who complete the study. SPSS version 28 was used to conduct this power analysis.

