#### 10.1.6 SAFETY OVERSIGHT

Safety oversight will be under the direction of a Data and Safety Monitoring Board (DSMB) composed of individuals with the following expertise and/or qualifications:

- Clinical knowledge of patient population and study intervention products, e.g., urologists, pharmacists, PM&R physicians treating patients with SCI, etc.
- Statistics
- Independent from the day-to-day study conduct

- Generally free of conflicts of interest (COI)
  - In the case of appearance of a COI or potential COI, we will put in place adequate measures and practices to minimize bias.

The DSMB will meet on an enrollment-based schedule. For every ten subjects which complete their 6-month intervention, the DSMB members will convene to assess safety and efficacy when appropriate, comparing data from the six-month period prior to enrollment with that obtained during the treatment period. The DSMB will operate under the rules of an approved charter that will be written and reviewed at the organizational meeting of the DSMB. At this time, each data element that the DSMB needs to assess will be clearly defined. The DSMB will provide its input to the study team and the Sponsor, when appropriate. They will be provided with periodical updates on study participants, AEs and SAEs as well as other issues encountered during the conduct of this trial.

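### The total-events safety trigger is diluted by UTI records, and the listed toxicity symptoms are never counted together; reporting totals with and without UTI events plus one grouped toxicity count is a minor, cheap improvement

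*Protocol*

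**What the plan says.** Protocol 9.4.4 (Safety Analyses) has the coordinator monitor event frequency and states that instances in which "the frequency of total events or of any event seem higher than expected will be referred to the DSMB". This trigger has two limbs: total events, or any single event. No expected rate or limit is given for either.

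Protocol 8.3.1 defines what enters the count. "This interpretation includes positive test results on urine analysis and urine culture", whether the study or the treating physician ordered the test, "and reports of UTI symptoms (e.g., malodorous and cloudy urine, fatigue, fever, chills, etc".

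Protocol 8.2 has suspected gentamicin toxicity assessed at the bi-weekly contacts. It names "new onset and prolonged numbness, skin tingling, dizziness, and vertigo", then muscle twitching, tinnitus, roaring in the ears and hearing loss: eight symptoms in all. Nothing asks for them to be counted as a group.

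Protocol 9.2 assumes "there will be a 50% reduction in UTIs from the number that participant experienced during the prior six months", and says "the sample size needed to have a power of at least 80% will be 15".

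Protocol 10.1.6 has the DSMB meet after every ten completers, "comparing data from the six-month period prior to enrollment with that obtained during the treatment period". Protocol 8.3.4 starts adverse event reporting at consent. The SAP describes no adverse event analysis.

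**The concern.** A trigger on total events is useful only if the total moves with harm. Here much of the total is likely to be the outcome the drug is meant to reduce. An effective drug lowers the count, and that fall can offset a rise in other events. The total-events limb is then least sensitive to toxicity when the drug works.

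The any-event limb is not offset by fewer UTIs, but it looks at one term at a time. A few participants with different ototoxic or neurotoxic symptoms may each add a single case to a separate line, and no line need look unusual.

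The comparison in 10.1.6 does not fill the gap. The UTI is the only event that the plan sets out to count both before and during treatment. There is no pre-treatment count of tingling, tinnitus or dizziness to compare with.

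At stake is how readily a modest, non-serious toxicity signal reaches the DSMB as a pattern.

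**Working it through.** **The plan's own figure.** Section 9.4.4 has none to reproduce. The nearest, 15 completers in 9.2, cannot be reproduced because no SD of the log-rate differences is given (two-sided, it implies about 0.89). That does not bear on this point; 15 is used only as the group size.

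**Inputs from the Protocol.** 15 completers (9.2); at least 2 UTIs each in the prior six months (5.1); a 50% fall (9.2); eight toxicity symptoms (8.2).

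**Assumptions, because the documents give no value.** One to three adverse event records per UTI. A limb fires when its count reaches the smallest number with Poisson upper-tail probability of at most 5% under the expected mean. Toxicity is spread evenly over the symptoms.

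**Step 1: room created by efficacy.** Prior UTIs: 15 × 2 = 30. On treatment: 30 × 0.5 = 15. The room before the total regains the prior level is 30 − 15 = 15 events at one record per UTI, 30 at two and 45 at three.

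**Step 2: total-events limb, one record per UTI, no other background.**

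| Expected total | Limit | No added events | 5 added (mean 20) | 15 added (mean 30) |
|---|---|---|---|---|
| Prior rate, 30 | 40 | <0.001 | <0.001 | 0.046 |
| Halved rate, 15 | 23 | 0.033 | 0.28 | 0.92 |

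The dilution is severe if the prior rate is taken as expected. It is much weaker if the expected total already allows for the fall.

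**Step 3: any-event limb, eight symptoms.** Let b be the expected count per symptom in the whole group and a the number of added events. Each symptom has mean b + a/8, and P(at least one symptom fires) = 1 − [P(count below limit)]^8. The grouped count has expected mean 8b and mean 8b + a with toxicity.

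- Example with b = 0.5 and a = 5: the limit is 3 and the mean is 0.5 + 0.625 = 1.125. P(count ≥ 3) = 1 − e^(−1.125)(1 + 1.125 + 0.633) = 0.105, and 1 − 0.895^8 = 0.59. Counting seven terms instead of eight gives 0.60.

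| b | Any-event: limit; a = 0, 3, 5 | Grouped: limit; a = 0, 3, 5 |
|---|---|---|
| 0.5 | 3; 0.11, 0.38, 0.59 | 9; 0.02, 0.27, 0.54 |
| 0.1 | 2; 0.04, 0.50, 0.76 | 3; 0.05, 0.73, 0.93 |
| 0.05 | 1; 0.33, 0.97, 0.995 | 3; 0.01, 0.66, 0.91 |

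At b = 0.1 the grouped count is clearly more sensitive at a similar false-alarm rate. At b = 0.5 its sensitivity is a little lower, but it gives about a fifth of the false alarms. At b = 0.05 one case of any symptom fires the any-event limb, which catches nearly everything but also fires a third of the time with no toxicity.

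If all five added events fall under one symptom with expected count 1, the limit is 4 and P(count ≥ 4 | mean 6) = 0.85. A concentrated signal is therefore likely to be seen.

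**Step 4: scatter.** Three cases over eight equally likely terms all differ with probability (8 × 7 × 6)/8³ = 0.66. For five cases it is (8 × 7 × 6 × 5 × 4)/8⁵ = 0.21.

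**Step 5: once-per-participant count.** With 15 participants, P(at least 2 affected) = 1 − (1 − p)^15 − 15p(1 − p)^14. This is 0.01 at p = 1%, 0.45 at 10% and 0.83 at 20%. The cut of 2 is for illustration only.

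**The case against.** A reader might infer that an effective drug could hide its own toxicity from the DSMB. The documents do not support that.

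- Section 9.4.4 is not the only frequency trigger. Section 8.3.5 separately sends any event that is more frequent than expected, or more severe than known, to the IRB and the DSMB.
- All SAEs go to the DSMB (8.3.6), as does information on deaths (9.4.4). The DSMB gets periodic adverse event updates (10.1.6) and has full access to study data (10.1.3).
- Toxicity symptoms are asked about by name at the bi-weekly contacts, and physician assessment is recommended for anyone who reports them (8.2). Individual follow-up does not wait for a pooled count.
- The trigger is a judgement, not a Poisson rule. Section 2.3.1 calls toxicity unlikely, so a single case of hearing loss might already seem higher than expected.
- Section 8.3.1 does not say that one UTI is logged three times, and 8.3.3.1 grades a UTI as one disorder.

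All of this stands, and it confines the point to small, scattered, non-serious excesses. It does not remove it. SAE reporting does not reach non-serious tingling or tinnitus. Section 8.3.5 is also per event and has no benchmark. Section 8.3.3.3 makes these symptoms expected because the Protocol lists them, so non-serious cases are not reported individually to the IRB. The updates in 10.1.6 specify neither an interval nor any grouping, and 15 completers bring only one scheduled meeting.

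A reader might also conclude that UTIs should come out of the trigger. That would be a trade-off, not a plain gain: 2.3.1 lists contamination and antibiotic resistance as risks, and a rise in UTIs is one way they could show.

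**Conclusion.** The point holds as a minor one. The total-events limb of 9.4.4 is diluted by the primary efficacy outcome. At the entry minimum of two prior UTIs and the assumed 50% fall, the dilution leaves room for 15 other events at one record per UTI, provided that expected means the prior level. A concentrated or serious signal would still reach the DSMB by other routes.

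The remaining gap is a small excess of non-serious symptoms spread over the 8.2 list. In the illustration, five such events go unflagged by the any-event limb with probability from under 1% to about 41%. The range is wide because the Protocol defines neither expected nor a limit, so these figures show the mechanism and do not predict what the DSMB would do. The prior-period comparison in 10.1.6 can inform on UTIs only; that follows directly from 8.3.4 and needs no assumption.

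**What to change.** Keep both limbs of 9.4.4 and the trigger in 8.3.5. In 9.4.4, and consistently in 8.3.5 and the DSMB charter:

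1. Report adverse event totals both with and without UTI-related events (UTI symptoms, positive urinalyses, positive cultures).
2. Add one count of participants with any symptom on the 8.2 toxicity list, each participant counted once.
3. State that the prior-six-months comparison in 10.1.6 covers UTIs only.

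Any referral number, and any action that follows from it, stays with the DSMB and the sponsor. Section 10.1.6 already has the data elements for DSMB review defined when the charter is set up, which is a natural place for this.

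The cost is a few sentences and one or two extra table rows per report, from the same data, staff and committee. Keeping UTIs in the existing triggers means that a rise in UTIs still prompts referral.
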